### **1.7 Exploratory Rationale**

Gene expression profiling and mutational analysis of laser micro dissected HRS cells will be performed to evaluate genes of interest. This will be performed on archival tissue blocks that must be submitted as described in the lab manual. Whenever possible the most recent biopsy sample must be sent for evaluation. If archival tissue is not available a fresh biopsy must be

performed prior to treatment with study drug. An excisional biopsy is preferred in all instances however, when an excisional biopsy is not possible a core biopsy will be allowed. If core biopsy is utilized then 4-6 cores must be provided for analysis to ensure adequate sample. In those patients who progress or do not respond to therapy, end of study (EOT) testing includes and optional, highly recommended tumor biopsy for assessment. In this instance excisional or core biopsy will be acceptable.

To assess ibrutinib's influence on T cell behavior and antitumor effect, serial serum samples pre and post therapy will be assessed for Th1 ( (IFN- $\gamma$  ) and Th2 cytokines ( IL-10, IL-4 and IL-13) at 4 distinct time points (pre-dose, cycle 1 day 2 , day 15, and day 28) . The cytokine profiles pre and post therapy with ibrutinib will be compared to assess modifications in T cell subsets due to ibrutinib therapy. In addition post treatment T cell populations will be compared with tumor microenvironment populations.

HL has shown sensitivity to T cell immune based anti-neoplastic therapy. A potential predictor of immune based therapy may be the presence of overexpression of the PDL1 and PDL2 proteins. Due to the potential of ibrutinib to alter alternative immunity through T cell subsets correlating responses to T cell alterations and malignant overexpression of PDL1 and PDL2 may be beneficial. Consequently, archived tissue will be evaluated by three probe FISH assay for relative copy gain or polysomy of chromosome 9p.11. This data will then be correlated with clinical activity of ibrutinib in cHL.

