### 2.3. Exploratory Objective(s)

- To assess the mechanism(s) by which ibrutinib may be active in patients with cHL by the correlation of potential biomarkers with clinical outcomes.

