## **9. STATISTICAL CONSIDERATIONS**

### **9.1. Objectives**

The primary objective is estimation of the overall response rate. Secondary objectives are estimation of duration of response and progression free survival. The exploratory objectives are identification of genes of interest, estimation of the T cell subset alteration and estimation of the association of PDL1 and PDL2 overexpression by FISH with overall response.

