### **9.3. Endpoints**

#### **9.3.1. Primary Endpoints**

- Overall Response Rate (ORR)**

Overall response rate (ORR) is defined as the proportion of participants having a complete (CR) and partial (PR) response.

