#### **9.3.3. Exploratory Endpoints**

The influence of ibrutinib on T cell behavior and antitumor effect will be assessed using pre-therapy and post therapy flow cytometry measures of Th1 and Th2 at predetermined time points in therapy.

PDL1 and PDL2 copy number analysis on paraffin-embedded tissue sections will be assessed by FISH.

All patients undergoing any exploratory evaluations will be assessed for correlative analysis.

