#### **9.4.3. Biomarker Analyses**

- Pre/Post Th1 Th2 Changes for ORR+ and ORR- individuals

McNemar's test will be used to evaluate the statistical significance of pre /post therapy changes in Th1 and Th2 positivity separately for those who have an ORR and for those who do not. A conditional logistic regression model will be used to explore whether pre-post changes in Th1 and Th2 are predictive of ORR.

- Association of PDL1 and PDL2 positivity with ORR

The association between PDL1 and PDL2 positivity will be explored using Fisher's exact test. A logistic regression model will be used to explore the association of PDL1 and PDL2 copy gain with ORR.

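### Section 9.4.3: the conditional logistic model for Th1/Th2 change has response as outcome but names no stratum, and with patient as stratum it estimates nothing

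*Combined protocol and SAP*

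**What the plan says.** Under the bullet "Pre/Post Th1 Th2 Changes for ORR+ and ORR- individuals", section 9.4.3 plans two analyses. The first is within-group: "McNemar's test will be used to evaluate the statistical significance of pre /post therapy changes in Th1 and Th2 positivity separately" for responders and for non-responders. The second is the regression: "A conditional logistic regression model will be used to explore whether pre-post changes in Th1 and Th2 are predictive of ORR". No stratum, matched set or other conditioning factor is given there or elsewhere. The next bullet of the same section uses plain logistic regression to relate PDL1/PDL2 copy gain to response.

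Section 9.3.1 says that the overall response rate is "defined as the proportion of participants having a complete (CR) and partial (PR) response", so each patient contributes one yes/no value. Section 9.2 describes a single-arm, single-stage study; no matching is mentioned.

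The aims bear on the point unevenly. Section 2.3 wants to study mechanism "by the correlation of potential biomarkers with clinical outcomes", and section 1.7 says that "correlating responses to T cell alterations and malignant overexpression of PDL1 and PDL2 may be beneficial". For T cells, section 9.1 lists only "estimation of the T cell subset alteration".

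**The concern.** A conditional logistic model learns only from sets in which the outcome varies. The sentence in 9.4.3 puts response on the outcome side, and the only natural set in this design is the patient. Response cannot vary within a patient, so on that reading the model returns nothing.

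The two McNemar tests cannot stand in for it. Each asks whether positivity changed within one response group. Neither asks whether the change differed between groups, and no other section supplies that comparison.

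What is at stake is limited. A model that drops every set would be noticed. The risk is that the replacement (outcome, stratum, row layout and which post-treatment sample) is then chosen with the data in view.

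**Working it through.** **Inputs.** 31 evaluable patients and the rule of 13 or more responders (section 9.5); null 30%, alternative 50%, type I error 10.69%, power 85% (Synopsis); 4 institutions (section 9.6); one response value per patient (section 9.3.1). Section 9.4.3 gives no figure of its own. The nearest design figure reproduces: P(X ≥ 13 | n = 31, p = 0.30) = 0.1069 and P(X ≥ 13 | n = 31, p = 0.50) = 0.859. It is used here only to set an illustrative split of 13 responders and 31 − 13 = 18 non-responders.

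**Step 1: patient as stratum, response as outcome.** For stratum i with rows j and k_i = Σ_j y_ij, the conditional likelihood is

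L_i(β) = exp(β Σ_j x_ij y_ij) / Σ_{c: |c| = k_i} exp(β Σ_{j∈c} x_ij).

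If both rows of a patient have y = 1, then k_i = 2 and the only subset of size 2 is the whole set, so L_i = 1. If both have y = 0, then k_i = 0, only the empty subset qualifies, and L_i = 1. With one row per patient (the change score) the same holds. The log-likelihood is therefore 0 for every β. On illustrative data it was exactly 0 at β = −5, −1, 0, 1 and 5, for both layouts. With two rows per patient the software dropped all 31 groups and 62 observations and gave no estimate.

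**Step 2: forms that do fit but are not stated.** One simulated data set (31 patients, 13 responders, pre/post correlation 0.5, 1 SD rise in responders; all but the 31 are assumptions), one row per patient:
- one stratum for everyone: 1.03 (SE 0.49);
- 4 equal site strata: 1.04 (SE 0.51);
- ordinary logistic regression: 1.07 (SE 0.50).

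The one-stratum form conditions on the total number of responders, so it nearly equals ordinary logistic regression.

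The reversed model takes positivity as outcome, patient as stratum, and time and time-by-response as terms. Only patients whose positivity flips contribute. The interaction is the log odds ratio of direction of flip by response. In a second illustrative data set 12 of 31 patients did not flip. The fit implies 7 up and 1 down in responders, and 7 up and 4 down in non-responders: log[(7/1)/(7/4)] = log 4 = 1.39, SE = √(1/7 + 1/1 + 1/7 + 1/4) = 1.24. A zero cell leaves no finite maximum-likelihood estimate.

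**Step 3: separate McNemar tests are not a comparison.** With assumed discordant counts:
- responders 8 v 1: p = 2(1 + 9)/2⁹ = 0.039;
- non-responders 6 v 2: p = 2(1 + 8 + 28)/2⁸ = 0.29;
- direct comparison, Fisher's exact test on [8, 1; 6, 2]: p = (56 + 252 + 84)/680 = 0.58.

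One test is significant and the other is not, yet the groups do not differ detectably.

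**Step 4: does the choice of repair matter for power?** Simulation, 1,500 runs per setting, 13 v 18, bivariate normal marker, non-responders unchanged, positivity cut at the baseline median, pre/post correlation 0.2/0.5/0.6. The difference is in SDs of the change. The documents give none of these values, so all are assumptions.

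| Analysis | 0.8 SD | 1.1 SD |
|---|---|---|
| Firth logistic, measured change | 0.54/0.55/0.55 | 0.83/0.81/0.82 |
| Firth logistic, change in positivity | 0.27/0.26/0.24 | 0.41/0.39/0.36 |
| Reversed model, penalised, positivity | 0.24/0.18/0.17 | 0.36/0.28/0.21 |

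The second row minus the third is 3, 8 and 7 points at 0.8 SD, and 5, 11 and 15 at 1.1 SD. A repeat gave about 3 to 9 and 4 to 12 points. Null rejection for the two positivity analyses was 0.04 to 0.06.

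**The case against.** **The failure depends on a stratum that the reader supplies.** The plan never says patient as stratum. Its predictor is already a change, naturally one value per patient, and conditioning on the total number of responders fits well. Exact logistic regression, one of the repairs below, is itself a conditional analysis of that kind. This stands. A reader might infer that the plan contains no workable comparison of responders with non-responders. The documents do not support that: they leave the stratum open, and several choices work. What they support is that the model is unspecified on the one element that defines it, and that the only pairing in the design is the choice that fails.

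**The intention can be guessed.** Conditional logistic regression is the usual regression extension of McNemar's test, and the bullet heading suits the reversed model. This stands in part. The sentence itself points the other way, because it treats response as the thing predicted. Two plausible intentions with different outcomes are a reason to write one down.

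**It is only exploratory.** Section 9.1 reserves association with response for PDL1/PDL2; for T cells it asks only for estimation of change, which the McNemar tests serve. The responder comparison has to be drawn from the broader wording of sections 1.7 and 2.3 and from the regression sentence itself. This stands and sets the severity.

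**Power.** A reader might infer that the candidate repairs differ several-fold in power, by setting Firth on measured change (0.53 to 0.56 at 0.8 SD) against the exact reversed model (0.08 to 0.17). That contrast mixes three things: measured change against dichotomised positivity, a conservative exact test (null rejection 0.02), and the model form. On like data with like fitting, the form accounts for a modest part.

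**Conclusion.** The concern holds as a minor specification error. Section 9.4.3 names a conditional model with response as outcome and no stratum. With patient as stratum it yields 0 informative sets out of 31; that is algebra and rests on no assumption beyond one response value per patient. It can be fitted only in forms that the plan does not state. The McNemar tests do not compare the response groups.

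The two penalised positivity repairs differ by about 3 to 9 points of power at 0.8 SD. At 1.1 SD the gap is about 4 to 12 points in one run and 5 to 15 in another. Using measured change in place of positivity is a separate gain (about 0.53 to 0.56 against 0.25 to 0.30 at 0.8 SD). These figures rest on the assumed effect sizes, correlations, normality, cut and 13 v 18 split. They also take 31 as the number analysed. Section 9.3.3 says "All patients undergoing any exploratory evaluations will be assessed for correlative analysis", but only patients with paired samples and an assessed response can enter.

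The failed fit would be visible. The primary response test, the sample size and the error rates are unaffected.

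**What to change.** Rewrite the regression sentence in 9.4.3 in one of two ways.

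1. Preferred: ordinary logistic regression, exact or Firth because responders will be few, of response on each patient's pre-to-post Th1/Th2 change, one row per patient.
2. If the conditional form was intended: Th1/Th2 positivity as outcome, patient as stratum, time and time-by-response as terms, with the interaction as the test of interest. Fit it by a penalised or exact method, because zero cells are likely (46 to 62% of simulated trials at 0.8 SD), and define positivity.

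Under either, name one on-treatment sample in advance. Do not use the progression sample in Appendix 1, footnote e: only patients who progress can supply it, so its availability depends on outcome. Add that the two McNemar p-values are not to be read as a between-group comparison, and label the results exploratory. Whether to analyse measured change or positivity is a separate decision that should also be written down.

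The cost is two or three sentences, with the same samples, assays and patients. Power stays modest with about 31 patients, so results remain hypothesis-generating.

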### **9.5. Sample Size Determination**

A study of 31 evaluable participants was deemed feasible. To accomplish this with an expected dropout not evaluable rate of 12%, a total sample population of 35 patients will be consented. We specified statistical power of 85% to distinguish a null hypothesis value of 30% against an alternative value of 50% assuming a binomial test of one proportion with a target, one-sided type error of 11%. Under these assumptions the null hypothesis will be rejected if there are 13 or more ORRs among the 31 participants.

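### The Fisher's exact test in 9.4.3 compares PDL1 with PDL2 and leaves out response, contrary to its own heading and to the objective in 9.1

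*Combined protocol and SAP*

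**What the plan says.** Section 9.4.3 (Biomarker Analyses) has a bullet headed "Association of PDL1 and PDL2 positivity with ORR". Two analyses follow. The first is: "The association between PDL1 and PDL2 positivity will be explored using Fisher's exact test". The second is: "A logistic regression model will be used to explore the association of PDL1 and PDL2 copy gain with ORR".

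Section 9.1 gives the matching exploratory objective as "estimation of the association of PDL1 and PDL2 overexpression by FISH with overall response". Section 1.7 says that "archived tissue will be evaluated by three probe FISH assay for relative copy gain or polysomy of chromosome 9p", and then: "This data will then be correlated with clinical activity of ibrutinib in cHL". Section 9.3.3 lists PDL1 and PDL2 copy number by FISH as the exploratory measure. The Statistical Methods part of the Synopsis mentions both FISH and IHC. No section defines positivity, and none gives a prevalence, a concordance between the markers, or a significance level for this test.

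**The concern.** A test of association needs the two variables whose association is in question. The heading and the objective pair each marker with response; the Fisher sentence pairs one marker with the other. No stated objective asks whether PDL1 status tracks PDL2 status.

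An analyst who follows the sentence will produce a PDL1-by-PDL2 table and report its p-value under a heading about ORR. If the markers tend to be gained together, which is plausible when section 1.7 describes one FISH assay of chromosome 9p, that p-value could well be small. A reader could then take it as evidence that the markers predict response to ibrutinib. An analyst who sees the problem and tests against ORR instead makes a sensible change, but one that departs from the written plan without a record.

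**Working it through.** **The texts side by side.**

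| Place | First variable | Second variable |
|---|---|---|
| 9.1 objective | PDL1/PDL2 overexpression by FISH | overall response |
| 1.7 rationale | FISH result | clinical activity |
| 9.4.3 heading | PDL1/PDL2 positivity | ORR |
| 9.4.3 Fisher sentence | PDL1 positivity | PDL2 positivity |
| 9.4.3 logistic sentence | PDL1/PDL2 copy gain | ORR |

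Only the Fisher sentence omits response. Section 1.7 has the markers read on archived tissue, or on a biopsy taken before study drug if there is none. A PDL1-by-PDL2 table therefore reflects the tumour before treatment, and nothing in it can change with the effect of ibrutinib.

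**Inputs.** The plan states no figure for this test, so there is none to reproduce. N = 31 comes from 9.5 ("A study of 31 evaluable participants was deemed feasible"). The primary design that uses it does reproduce: rejecting at 13 or more of 31 gives an exact one-sided error of 0.1069 (Synopsis: 10.69%) and power of 0.859 (stated: 85%).

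Assumptions that are not in the documents: two-sided 5% level, usable tissue from all 31, equal prevalence p for both markers, and discordance split evenly.

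**The test as written.** With concordance c, let d = (1 − c)/2. The cell probabilities are p − d (both positive), d and d (one positive), and 1 − p − d (both negative). For example, p = 0.5 and c = 0.8 give d = 0.1 and cells 0.4, 0.1, 0.1, 0.4. The rejection rate is the summed multinomial probability of all tables of 31 patients with Fisher p ≤ 0.05. There are 34·33·32/6 = 5,984 possible tables, so the sum is exact.

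| Prevalence | c = 100% | c = 95% | c = 90% | c = 80% |
|---|---|---|---|---|
| 30% or 70% | 100% | 99.9% | 99% | 76% |
| 50% | 100% | 100% | 99.9% | 91% |
| 80% | 99.9% | 98% | 90% | 42% |
| 90% | 96% | 71% | 38% | 0% |
| 95% | 80% | 25% | 0% | not possible |

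The c = 100% column can be checked by hand. If all 31 tumours are positive for both markers, p = 1. If exactly one is negative for both, p = 1/31 = 0.032, which is already significant; with two, p = 1/465 = 0.002. So at 90% prevalence the rate is essentially 1 − 0.9^31 = 0.96, and at 95% it is 1 − 0.95^31 = 0.80. If the markers were independent, the rate would be 0.6% to 3% across these prevalences.

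**The test as presumably intended (one marker against ORR).** With ORR 50% in marker-positive and marker-negative patients alike, the rejection rate is 1% to 3%. Where ORR differs:

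| ORR, marker-positive v marker-negative | Power, prevalence 30–70% | Power, prevalence 90% |
|---|---|---|
| 60% v 40% | 12–14% | 5% |
| 70% v 30% | 45–52% | 18% |
| 80% v 20% | 85–91% | 45% |

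The reworded test responds to the question asked, but at this sample size only very large differences are likely to be detected.

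**The case against.** The strongest reply is that this is a drafting slip. The heading directly above supplies the missing words, and most statisticians would read ORR into the sentence. That is probably what was meant. It explains the sentence without making it correct, and a pre-specified analysis should not depend on the analyst's guess.

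A reader might infer that the biomarker objective has no valid analysis. The documents do not support that. The logistic regression in the next sentence relates copy gain to ORR, and both 9.1 and 9.3.3 define the marker by FISH. If positivity means FISH copy gain, a logistic model with one binary marker examines the same association as the 2×2 table against response. If positivity means something else, such as IHC, the comparison named in the heading is specified nowhere, but the argument that one assay makes the markers concordant is then weaker. Because positivity is undefined, neither reading can be assumed.

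A reader might also infer that the test would be significant almost whatever happens. That needs high concordance and a prevalence that is not extreme. The documents give neither, and the table shows rates well below 50% for several combinations at prevalence 80% or more. That the result cannot depend on response needs no simulation: response is not in the table.

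One could go further and ask for the logistic model to be fitted one marker at a time. That is a modelling preference; nothing in the logistic sentence is shown to be wrong.

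**Conclusion.** The Fisher sentence is wrong as written. It omits the outcome, contradicts its own heading and the objective in 9.1, and answers no stated question. That conclusion rests on the text alone and holds at any prevalence or concordance.

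The chance of a misleading small p-value is conditional. It is about 76–100% at prevalence 30–70% with concordance 80–95%, and falls to 71%, 38% and 0% at prevalence 90% with concordance 95%, 90% and 80%, all under the assumptions listed above.

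Severity is low. The analysis is exploratory, no decision rule hangs on it, the logistic model already addresses the FISH-based objective, and the primary ORR test is untouched.

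**What to change.** Replace the Fisher sentence in 9.4.3 with: *PDL1 positivity and PDL2 positivity will each be compared with response status (CR or PR versus neither) by Fisher's exact test.*

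Add one sentence saying whether positivity means FISH copy gain or another measure, and with what cut-off, so that the Synopsis (FISH and IHC), 9.3.3 (FISH) and 9.4.3 agree. Because power is low at about 31 patients, it would help to report ORR by marker status with confidence intervals beside the p-values.

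The cost is a few lines of text. No new data, samples or patients are needed, and the primary analysis does not change.

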### **9.5. Sample Size Determination**

A study of 31 evaluable participants was deemed feasible. To accomplish this with an expected dropout not evaluable rate of 12%, a total sample population of 35 patients will be consented. We specified statistical power of 85% to distinguish a null hypothesis value of 30% against an alternative value of 50% assuming a binomial test of one proportion with a target, one-sided type error of 11%. Under these assumptions the null hypothesis will be rejected if there are 13 or more ORRs among the 31 participants.

### **9.6 Accrual Rate, Accrual Duration and Expected Study Duration**

The expected accrual rate across the 4 institutions is 35 participants per year. Thus it is expected that the duration of accrual will be one year. An additional year is planned for evaluation of the primary, secondary and safety endpoints.

## **10. ADVERSE EVENT REPORTING**

Timely, accurate, and complete reporting and analysis of safety information from clinical studies are crucial for the protection of subjects, investigators, and the sponsor, and are mandated by regulatory agencies worldwide.

### 10.1.1 Adverse Events

An AE is any untoward medical occurrence in a subject administered a pharmaceutical product and which does not necessarily have a causal relationship with this treatment. An AE can therefore be any unfavorable and unintended sign (including a clinically significant abnormal laboratory finding, for example), symptom, or disease temporally associated with the use of an investigational study drug, whether or not considered related to the study drug ([ICH-E2A, 1995](#)).

For the purposes of this clinical study, AEs include events which are either new or represent detectable exacerbations of pre-existing conditions.

The term “disease progression” should not be reported as an adverse event term. As an example, “worsening of underlying disease” or the clinical diagnosis that is associated with disease progression should be reported.

Adverse events may include, but are not limited to:

- Subjective or objective symptoms provided by the subject and/or observed by the Investigator or study staff including laboratory abnormalities of clinical significance.
- Any AEs experienced by the subject through the completion of final study procedures.
- AEs not previously observed in the subject that emerge during the protocol-specified AE reporting period, including signs or symptoms associated with the underlying disease that were not present before the AE reporting period
- Complications that occur as a result of protocol-mandated interventions (e.g. invasive procedures such as biopsies).

The following are NOT considered AEs:

- **Pre-existing condition:** A pre-existing condition (documented on the medical history CRF) is not considered an AE unless the severity, frequency, or character of the event worsens during the study period.
- **Pre-planned or elective hospitalization:** A hospitalization planned before signing the informed consent form is not considered an SAE, but rather a therapeutic intervention. However, if during the pre-planned hospitalization an event occurs, which prolongs the hospitalization or meets any other SAE criteria, the event will be considered an SAE. Surgeries or interventions that were under consideration, but not performed before enrollment in the study, will not be considered serious if they are performed after enrollment in the study for a condition that has not changed from its baseline level. Elective hospitalizations for social reasons, solely for the administration of chemotherapy, or due to long travel distances are also not SAEs.

- **Diagnostic Testing and Procedures:** Testing and procedures should not be reported as AEs or SAEs, but rather the cause for the test or procedure should be reported.
- ***Asymptomatic Treatment Related Lymphocytosis:*** *This event should also not be considered an AE. Subjects with treatment-related lymphocytosis should remain on study treatment and continue with all study-related procedures.*

